### 3.6 Procedure

Providers and patients are consented by the assessment team prior to participation. All participants are informed that they can withdraw from the study at any time. All patients are compensated for their participation, and providers are compensated if permitted by their CMHC. The assessments are completed by the assessment team, comprised of experienced assessors. Note that assessors complete the consent process to minimize burden on participants (e.g., this practice reduces number of calls from team). Because the assessors need to provide study-related information—such as number of assessments and treatment sessions—to the patients during the consent process, the assessors are not blind to condition at pre-treatment. However, at post-treatment and 6FU, we endeavor to keep assessors blind to condition. As is common in clinical trials, there are ways that assessors may be able to infer treatment condition (e.g., slightly different assessment batteries, patients may ask assessors “when does treatment start?” during the post-delay assessment). Assessors receive ongoing supervision and are thoroughly trained to deliver the surveys with integrity and minimal bias.

#### 3.6.1 Providers

Provider assessments are completed after TranS-C training, at mid-treatment, and at post-treatment. See Figure 4 for provider timeline.

#### 3.6.2 Patients

Patient assessments in the immediate TranS-C treatment conditions are completed at pre-treatment, mid-treatment, post-treatment, and six months after treatment (6FU). Patient assessments in the UC-DT

condition are completed at pre-treatment and four or eight weeks after pre-treatment (i.e., post UC-DT), depending on whether their county has been randomized to Adapted or Standard TranS-C, respectively. After the post UC-DT assessment, patients start delayed treatment with TranS-C. They subsequently complete assessments at mid-treatment, post-treatment, and 6FU. Note that patients do not complete a 6FU assessment after the delayed portion of UC-DT. This was a compromise made with CMCH partners, so that patients would not need to wait 7-8 months to receive treatment. See Figure 2 for patient timeline.

### 3.7 Allocation

CMHCs and patients are randomized through a computerized randomization sequence. We do not stratify during randomizing at the county level. When randomizing patients, we stratify for presence of psychosis or not (current), presence of substance use or not (current) and age ( $\geq 50$  or not), as there is evidence these variables can impact sleep or treatment outcome [50, 83, 84]. Only the facilitators, assessors, and research team (i.e., not CMHCs, providers, or patients) are privy to which CMHCs and patients are allocated to which TranS-C treatment condition (Adapted versus Standard TranS-C). CMHC providers and patients know whether their patients have been randomized to receive the immediate or delayed treatment. The facilitator informs each provider when they can start having sessions. In the immediate condition, the provider is asked to begin sessions as soon as possible. In the delayed condition, the provider is asked to wait until after the patient has completed the post-delay assessment (i.e., approximately four weeks in the Adapted condition or eight weeks in the Standard condition).

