### 3.9 Data Management and Dissemination

All patient-identifiable data are saved by the assessment team on password-protected fillable PDFs on a secure password-protected and HIPAA-compliant website. On these PDFs, patients and providers are assigned identification numbers. These identification numbers are then used to link anonymized data that is collected via password-protected Qualtrics. When collecting assessments, assessors call participants and enter the data into Qualtrics. Participants also have the option of entering their data directly into a

participant-facing version of the surveys via a HIPAA-compliant version of Qualtrics. Patient-identifiable data is not shared with outside entities during or after the trial. A data management team supervised by the PI, biostatistician (LD), and postdoctoral scholar (LDS) is responsible for downloading, collating, and analyzing the data.

A Data Safety Monitoring Board has been formed to help prevent and manage adverse events. The board includes members with expertise in SMI, psychosocial treatments, and randomized controlled trials. Members are independent from the PI and competing interests. A report was made to the board bi-annually for the first year of the research. Since then, it has shifted to annual reports. However, if safety issues arise, it will be changed to monthly meetings. Yearly reports are submitted to the Committee for the Protection of Human Subjects at UC Berkeley and National Institute of Mental Health.

Outcomes specifically of interest to our partners are presented to CMHC leadership as part of the widely-used implementation strategy, audit and feedback [92]. However, these interim analyses are used only for facilitation purposes. In other words, they do not influence research procedures in any way (e.g., to inform when to terminate the trial).

Results from the trial, as well as analysis code, will be shared via peer-reviewed publications, professional conference presentations, and meetings and newsletters to CMHCs, as relevant. Other than the authors and compliance with data-sharing agreements stipulated by the National Institutes of Health, no other entities have contractual agreements to access the final dataset. Deidentified data are submitted to the National Institute of Mental Health Data Archive twice per year, per their requirements.

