### **3.11 Changes to Preregistration**

In December 2022, updates relevant to the present protocol were made to the clinicaltrials.gov protocol (identifier: NCT04154631). These updates can be summarized as follows. First, minor changes were made to four inclusion and exclusion criteria, based on feasibility and preferred practices of CMHC partners. For instance, as described above, CMHCs preferred to determine which providers were eligible to deliver TranS-C, and thus, providers held a wider range of positions than we had originally anticipated. Additionally, in rare cases, providers outside of CMHCs participated in the study (e.g., a supervisee from a CMHC provider's private practice participated). Thus, we changed the provider criteria to be more inclusive (see provider inclusion criterion 1 above). Second, as the study unfolded, rich data emerged. To maximize the resources invested in this study, we decided to systematically capture these data with additional measures, now included in the 'Other Measures' section of clinicaltrials.gov. For example, the number of sessions delivered to each enrolled patient per provider was already being logged by the

facilitators. These data will be included in the dropout calculations and sensitivity analyses of the Implementation Phase main aims (see Measures and Planned Analyses). Third, as described above, to maximize recruitment goals, additional CMHC sites were recruited from new counties on an ongoing basis. We have added these additional sites/counties to clinicaltrials.gov. Fourth, the sample size has been changed to match the power analysis described above. The sample size in the original clinicaltrials.gov preregistration reflected a request from one reviewer of the National Institute of Mental Health grant to increase the sample size to account for a higher rate of dropout. However, this was deemed to be unfeasible, and the recruitment goal was adjusted to reflect the power analysis. Fifth, the type of design was corrected to be hybrid type 2, given the equal emphasis on determining effectiveness of an intervention (i.e., TranS-C) and feasibility/impact of an implementation strategy (i.e., adapting interventions to fit context) [48, 49]. Sixth, after launching the study, we received requests to minimize burden for patients. In response, assessors began consenting patients during pre-treatment assessments. Thus, we now specify that assessors are blind to condition at post-treatment and 6FU.

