First, we did not collect data from leadership at our partner CMHCs. The primary reason was that these leaders have many demands on their time and already had generously collaborated with us on the design and implementation of the study. However, we recognize that leadership-level factors can meaningfully impact implementation outcomes [109]. Thus, exploring leadership perspectives on TranS-C will be an important direction for future research. Second, we considered additional assessment methods for sleep and circadian problems, such as a diagnostic interview (e.g., the Duke Structured Interview for Sleep Disorders; [63]) and polysomnography. However, even without these more intensive diagnostic tools, some patients reported difficulty with the length of assessments. Additionally, we were interested in recruiting patients with a broad range of symptom severity, which may have more ecological validity than a more restricted sample. That said, we acknowledge that there are certain outcomes that we will not be able to address due to this design choice (e.g., change in diagnostic status). Third, assessors are not blind to treatment condition at pre-treatment. To minimize burden on participants (e.g., reduce number of calls from team), assessors are in charge of the consent process, and therefore, they need to provide study-related information—such as number of assessments and treatment sessions—to the patients. At post-treatment and 6FU, we endeavor to keep the assessors blind but, as is common in clinical trials, there are ways that assessors may be able to infer treatment condition (e.g., slightly different assessment batteries). In rare instances, patients in the UC-DT condition ask assessors questions such as “when does treatment start?” or “when will I receive the workbook?” during the post-delay assessment. In such instances, the assessor may be able to ascertain that the patient has been assigned to the UC-DT condition. Assessors receive ongoing supervision and are thoroughly trained to deliver the surveys with integrity and minimal bias. Additionally, relative to interviews or clinical rating scales, the standardized surveys delivered by assessors are likely less vulnerable to bias (see Measures above). However, it is possible that assessor knowledge or hunches about patients’ condition may influence patient responses. Fourth, in the UC-DT condition, patients did not complete a 6FU assessment after the delay. This was a compromise made with CMCH partners, so that patients would not need to wait 7 to 8 months to receive treatment. Thus, analyses comparing TranS-C with UC-DT will evaluate outcomes from pre- to post-treatment, whereas analyses comparing Adapted versus Standard TranS-C can evaluate outcomes from pre- to post-treatment *and* pre- to 6FU. Depending on the outcomes from the trial, an important direction for future research will be testing the long-term effects of TranS-C relative to a control (e.g., UC-DT). Fifth, unforeseen challenges arose related to the COVID-19 pandemic and subsequent mandates in California (e.g., shelter-in-place). For some patients, sleep and circadian treatment became secondary to coping with other mental health ramifications of the pandemic (e.g., anxiety, isolation, grief) or even meeting basic needs of secure access to food and shelter [110]. Additionally, providers suddenly had more demands on their time, such as navigating the shift from in-person to virtual care—a shift that was also challenging for some patients. These changes had implications for the present study. For instance, we did not design the study to systematically evaluate potential differences in TranS-C delivery (i.e., in-person versus virtual versus phone). As another example, there was substantial turnover in providers and patients, leading to more discontinuity across treatment than anticipated. Sixth, some design choices were made to respect the expertise and preferences of our CMHC partners. For example, providers had the option to deliver TranS-C in a group or individual format. Even though this introduced variance into the study, it has been critical to the CMHCs, providers, and patients that we balance rigor with flexibility. We deliberated about whether to control for these variations necessitated by COVID-19 and the CMHC contexts. Ultimately, we decided against a prespecifying a comprehensive list of possible covariates, given the statistical drawbacks of controlling for many variables (e.g., [94-97]). At the conclusion of the trial, the sources of variation that resulted from the COVID-19 pandemic and needs/preferences of our community partners will be carefully considered as to whether they should be included as covariates.

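### Assessors are stated to be blind at post-treatment and six-month follow-up, but section 3.7 gives them the Adapted/Standard allocation, so that blinding does not hold for Adapted versus Standard

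*Combined protocol and SAP*

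**What the plan says.** Four places in the combined protocol and SAP bear on assessor blinding.

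- **Section 3.7 (Allocation)**: "Only the facilitators, assessors, and research team (i.e., not CMHCs, providers, or patients) are privy to which CMHCs and patients". The sentence goes on to make clear that the allocation meant is Adapted or Standard. No visit or period limits this.
- **Section 3.11 (Changes to Preregistration)**, in flat terms: "Thus, we now specify that assessors are blind to condition at post-treatment and 6FU".
- **Section 3.6 (Procedure)**, more cautiously: "However, at post-treatment and 6FU, we endeavor to keep assessors blind to condition". It adds that assessors are unblinded at pre-treatment because they run consent, and that later they may be able to guess the condition.
- **Section 5 (Discussion)**, as a limitation: "At post-treatment and 6FU, we endeavor to keep the assessors blind but, as is common in clinical trials", followed by examples of how an assessor might work out the condition and an acknowledgement that this could affect responses.

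Section 3.9 says that assessors telephone participants and key in the answers, with the alternative of a "participant-facing version of the surveys via a HIPAA-compliant version of Qualtrics". Section 3.10 gives the assessment team the evaluation of both patients and providers.

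**The concern.** A reader of section 3.11 would take outcome collection at post-treatment and 6FU to be blind to every arm of the trial. Section 3.7 says that the people collecting those outcomes hold one of the two allocations. The outcomes are self-reports, but they are often taken over the telephone by an assessor, and the Discussion accepts that an assessor's knowledge may affect the answers. A report that repeats the flat statement would credit the Adapted/Standard results with a protection the design does not provide. The existing limitation would not correct this. It covers knowledge at pre-treatment and occasional inference later, but not the fact that assessors are given the Adapted/Standard allocation.

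**Working it through.** The point has no numerical content, so the check is a comparison of the texts.

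**1. Does condition, as used in the blinding statements, include Adapted versus Standard?** Section 3.6 says assessors are unblinded at pre-treatment because they must tell patients how many assessments and sessions to expect.

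- Sessions number eight in Standard (section 3.4.1) and four in Adapted (section 3.4.2). UC-DT patients later receive their county's version (section 3.4.3), so the session count separates Adapted from Standard and not immediate from delayed.
- Assessments number four in the immediate arm (pre, mid, post, 6FU) and five in UC-DT (pre, post-delay, mid, post, 6FU), by section 3.6.2. That count separates immediate from delayed.

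The protocol's own reason for unblinding therefore covers both allocations.

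**2. Could the knowledge lapse after pre-treatment?** The note to Table 1 says Adapted/Standard is allocated by county. An assessor who knows the version for one patient knows it for every patient in that county, at every visit. In UC-DT the post-delay visit falls at four or eight weeks according to version (section 3.6.2), so scheduling also shows it.

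**3. Which contrast does blinding at 6FU serve?** Section 4.1 restricts TranS-C versus UC-DT to pre- to post-treatment. Only Adapted versus Standard uses 6FU (sections 4.1, 4.5 and 4.7). The 6FU claim therefore concerns the contrast whose allocation assessors are said to know.

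**4. Does any text reconcile the statements?** I found none that limits section 3.7 to pre-treatment, assigns uninformed assessors to later visits, or defines condition as immediate versus delayed only.

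**5. Result by contrast**

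| Contrast and outcomes | Visits | What the documents say | Result |
|---|---|---|---|
| Adapted vs Standard, patient outcomes (Aim 3, Exploratory Aim 1) | Post-treatment, 6FU | 3.7: assessors know; 3.11: assessors blind | Contradicted |
| Adapted vs Standard, provider ratings (Aim 2) | After training, mid- and post-treatment | 3.7: assessors know; no express blinding claim | Not blind, but no claim is contradicted |
| TranS-C vs UC-DT, patient outcomes (Aim 1) | Post-treatment or post-delay | 3.6: known at pre-treatment, may be inferred later; 3.7 does not say assessors know this allocation | Weakened, not contradicted |

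**The case against.** The strongest reply is that the limitation is already disclosed. Sections 3.6 and 5 claim only an effort to blind, and the flat wording appears only in a summary of registry changes. The Discussion also notes, fairly, that standardized surveys are less open to assessor influence than interviews or clinical ratings, and self-entry is available. This limits the likely harm. It does not remove the conflict, because guessing an arm and being told it are different things and only the first is disclosed.

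One might also read condition as immediate versus UC-DT only, since the patient questions given as examples concern the delay. Steps 1 and 3 count against that reading: the session count identifies the version, and no planned analysis compares immediate with UC-DT at 6FU.

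Four stronger conclusions may tempt a reader, and the documents do not support them.

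- *Blinding fails for both primary outcomes.* Sleep disturbance is primary for TranS-C versus UC-DT. The sentence in section 3.7 covers Adapted versus Standard only. The next one says that providers and patients know immediate or delayed, and does not mention assessors.
- *Provider acceptability was promised blind assessment.* The statements are framed around patient consent and name 6FU, a visit that providers do not have.
- *The assessor who consents a patient also collects that patient's outcome.* The documents do not describe the rota, so this is neither established nor excluded.
- *A false-positive rate can be attached to the problem.* That would need an assumed shift in responses, for which the documents give no basis. The planned 240 per arm in section 3.8 is the immediate versus UC-DT split, not Adapted versus Standard.

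**Conclusion.** The point holds for Adapted versus Standard. A blinding property is stated that section 3.7 says the design does not have, and it affects the patient outcomes of Aim 3 and Exploratory Aim 1 at post-treatment and 6FU. Aim 2 ratings are gathered by a team that knows the arm, which should be reported although no blinding was claimed. For Aim 1, the position is the one sections 3.6 and 5 already describe: imperfect blinding, with the risk disclosed.

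This rests on reading section 3.7 as written, without an unstated time limit. Nothing here shows that any outcome is biased, and the size of any effect cannot be derived from the documents. It should be corrected before results are reported, but it does not call the design of Aim 1 into question.

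**What to change.** 1. **Reconcile sections 3.6, 3.7, 3.11 and 5.** State, for each contrast and visit, to what assessors are blind. Say that they are not blind to Adapted versus Standard, extend the Discussion limitation to cover it, and carry the same wording into the registry entry and reports.
2. **Protect what can still be protected.** For remaining post-treatment and post-delay visits, where the rota allows, use an existing assessor who did not consent that patient. This helps blinding to immediate versus UC-DT only; it cannot restore blinding to a county-level allocation. Section 6 puts the end of recruitment at August 2022 and the last assessments at August 2023. With a delay of at most eight weeks, few post-delay visits may be left; the documents do not give the number.
3. **Record** any unblinding and whether each survey was taken by telephone or self-entered.

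The cost is some rota effort, two extra data items and a less favourable blinding statement. No additional staff are needed.

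I would not make self-entry the default at this stage, because that would confound mode with visit and calendar time. Nor would I rerun the primary analyses in self-entered data alone, because patients choose the mode after randomization and the subset would be self-selected.

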### 3.8 Sample Size

Sample size was determined via power analyses with Optimal Design [85, 86] and Stata 15 [87] and a two-sided alpha of 0.05. We used the original  $N = 8$  counties that agreed to participate, though as noted above, new counties have since been recruited to meet sample size goals determined by the following calculations. For Aims 1 and 3, 60 patients from eight randomized clusters/CMHCs was found to provide over 90% power to detect large effects (average  $d=0.89$  from [35]) between TranS-C and UC-DT, and over 80% power to detect a medium effect ( $d=0.50$ ) between Standard and Adapted TranS-C. For Aim 2, based on a prior study with a similar aim/measure [88], we expected a large effect size ( $d=0.80$ ) between Standard and Adapted TranS-C on the primary outcome of acceptability. Prior studies have reported high correlation coefficients between acceptability, feasibility, and appropriateness ( $rs=.67-.90$ ) [75, 89], thus the analysis for acceptability was expected to sufficiently power the other outcomes. Based on the site intra-class correlation (ICC) estimated from similar prior studies [90, 91], we assumed the ICC to be 0.01 and the inflation factor was calculated as  $1+(n-1)\times ICC$ . Eight clusters with an average cluster size of 10 was found to be needed to achieve over 80% power to detect a large effect for the outcome (acceptability) at the provider level. Thus, to test this aim, we would need at least 80 CMHC providers: 10 providers from 8 CMHCs (at least 4 CMHCs per randomized arm).

In sum, we aimed to randomize at least eight CMHC clinics to either Standard or Adapted TranS-C, with at least 80 providers (10 per CMHC). The goal for patients is 240 patients (30 per CMHC) randomized to immediate Standard or Adapted TranS-C and 240 randomized to UC-DT (30 per CMHC). Adding 20% to account for attrition, the total target sample size for providers is 96 and for patients is 576.

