## 2 AIMS

Together, the goal of the present hybrid type 2 effectiveness-implementation study [48, 49] is to evaluate the implementation and effectiveness outcomes of TranS-C in CMHCs of counties across California in the United States. The study will be conducted in three phases. This protocol will focus on Phase 1, the Implementation Phase, during which TranS-C is implemented in CMHCs via facilitation (see Method). Phase 2 is the Train-the-Trainer Phase, during which CMHC providers learn to train and supervise their peers in the delivery of TranS-C. Phase 3 is the Sustainment Phase, during which we will assess the extent to which TranS-C activities are sustained after facilitation has ceased.

During the Implementation Phase, sites are cluster-randomized by county to Adapted TranS-C or Standard TranS-C with 1:1 allocation. Then, within each county, patients are randomized to immediate TranS-C or UC-DT. The first aim is to assess the effectiveness of TranS-C, compared to UC-DT. We hypothesize that, compared to UC-DT, TranS-C (combined Adapted and Standard) will be associated with larger reductions in the primary patient outcome of sleep disturbance and the secondary patient outcomes of sleep-related impairment, functional impairment, and psychiatric symptoms. We also hypothesize that TranS-C's benefits for functional impairment and psychiatric symptoms will be mediated by improvements in sleep and circadian problems. The second aim is to evaluate whether TranS-C treatment condition (Adapted versus Standard TranS-C) is associated with fit to the CMHC context, operationalized as provider ratings of acceptability, appropriateness, and feasibility. We hypothesize that

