Adapted TranS-C will be superior to Standard TranS-C with respect to the primary provider outcome of acceptability and the secondary provider outcomes of appropriateness and feasibility. The third aim is to evaluate whether better fit mediates the relation between TranS-C treatment condition and patient outcome. We hypothesize that relative to Standard TranS-C, Adapted TranS-C will be associated with greater reductions in the primary and secondary patient outcomes indirectly through higher provider ratings of acceptability, appropriateness, and feasibility. Exploratory analyses will: (1) compare Adapted and Standard TranS-C on patient perceptions of credibility/improvement and select PhenX Toolkit outcomes; and (2) determine whether treatment effects are moderated by risk factors including age, sex, and sleep and circadian and psychiatric symptoms at baseline [50, 51].

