#### **4.5 Aim 3: Fit as a Mediator of Treatment Condition and Patient Outcome**

Multilevel structural equation modeling will be used to test whether improved perceptions of fit (i.e., acceptability, appropriateness, and feasibility) mediate the relation between TranS-C treatment condition (i.e., Adapted versus Standard TranS-C) and change in the primary patient outcome of sleep disturbance and the secondary patient outcomes of sleep-related impairment, functional impairment, and psychiatric symptoms. Models will evaluate change in outcomes from pre-treatment to post-treatment and pre-treatment to 6FU.

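### The power that section 3.8 credits to Aim 3 is for a difference between arms, whereas Aim 3 tests an indirect effect through fit, for which no power is reported

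*Combined protocol and SAP*

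**What the plan says.** Section 3.8 opens its patient calculation with "For Aims 1 and 3, 60 patients from eight randomized clusters/CMHCs was found to provide over 90% power to detect large effects". The same sentence goes on to claim "over 80% power to detect a medium effect", d=0.50, for Standard against Adapted TranS-C. The summary that follows splits the patients by timing of treatment: "The goal for patients is 240 patients (30 per CMHC) randomized to immediate Standard or Adapted TranS-C and 240 randomized to UC-DT", again 30 per CMHC. For Aim 2 the section assumes d=0.80 on acceptability, an ICC of 0.01 and eight clusters of 10 providers, and claims over 80% power.

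Section 2 defines the aim: "The third aim is to evaluate whether better fit mediates the relation between TranS-C treatment condition and patient outcome". Its hypothesis is that "Adapted TranS-C will be associated with greater reductions in the primary and secondary patient outcomes indirectly through higher provider ratings of acceptability", appropriateness and feasibility. The analysis in section 4.5 matches this: "Multilevel structural equation modeling will be used to test whether improved perceptions of fit" carry the effect of condition to patient outcome. It adds: "Models will evaluate change in outcomes from pre-treatment to post-treatment and pre-treatment to 6FU".

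On the design, section 2 says that "sites are cluster-randomized by county to Adapted TranS-C or Standard TranS-C with 1:1 allocation". Section 3.3.1 lists ten participating counties. Section 4.1 puts county into every model as a set of indicator variables, because there are few clusters.

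**The concern.** The power claim and the aim refer to different quantities. Power for the Adapted versus Standard difference concerns the total effect on patient outcome. Power for an indirect effect depends on two other quantities: how far condition shifts fit, and how strongly fit predicts outcome. Section 3.8 covers the first through Aim 2 and is silent on the second.

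As the section stands, a reader who meets a non-significant indirect effect could take it as adequately powered evidence against mediation. Aim 3 is one of the three main aims and carries the argument in section 5 about whether improved fit leads to better patient outcomes.

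A second issue affects the same contrast. Condition does not vary within county, so county dummies absorb it, and the precision attached to any Adapted versus Standard estimate depends on how counties are handled.

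**Working it through.** **1. The plan's between-arm figure.** Inputs from section 3.8: two-sided alpha 0.05, J=8 clusters (4 per arm), d=0.50, inflation 1+(n−1)×ICC. The ICC of 0.01 is stated for Aim 2; I assume it for patients. I read 60 patients as 60 per cluster (30 immediate plus 30 delayed), because 60 in total would give only about 35% to 49% power at d=0.50.

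SE = sqrt(4 × [1+(n−1)×ICC] / (J×n)); power from the non-central t on J−2 = 6 df, or from the normal approximation.

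- n=30: inflation 1.29, SE = sqrt(4×1.29/240) = 0.147, d/SE = 3.41. Power is 81.0% (t) or 92.6% (normal).
- n=60: inflation 1.59, SE = sqrt(4×1.59/480) = 0.115, d/SE = 4.34. Power is 94.8% (t) or 99.1% (normal).
- For ICC 0 to 0.02: 89.4% to 72.9% (t) at n=30, and 99.4% to 86.8% (t) at n=60.

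At ICC 0.01 the claim of over 80% reproduces with either count, so the figure alone does not show whether delayed-arm patients are included.

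**2. The condition-to-fit path.** d=0.80, n=10, ICC 0.01: inflation 1.09, SE = sqrt(4×1.09/80) = 0.233, d/SE = 3.43. Power is 81.3% (t) or 92.9% (normal). An indirect effect judged by joint significance cannot have more power than this path, so about 81% is the ceiling under the t test.

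**3. The indirect effect (illustration only).** The documents give no fit-to-outcome value, so I assume 0.1 to 0.4 SD of outcome per SD of fit. Simulation: 8 counties, 10 providers each, 3 or 6 patients per provider, ICC 0.01 for fit and outcome, no direct effect, 4000 runs per cell, joint significance, condition-to-fit tested on county means with 6 df.

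| Assumed path | 30 per county | 60 per county |
|---|---|---|
| 0.1 | 25.5% | 43.8% |
| 0.2 | 66.9% | 80.6% |
| 0.3 | 80.1% | 81.2% |
| 0.4 | 81.1% | 81.1% |

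Simulation error is about 0.6 points near 80%. Adding a provider-level variance share of 0.05 (2000 runs) lowers the first cell to 23.8%. With a normal test for the condition-to-fit path the range is 28.6% to 93.0% at 30 per county and 49.8% to 92.6% at 60.

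The case most favourable to the plan keeps the total effect at d=0.50. Full mediation then needs a path of 0.50/0.80 = 0.625, and half mediation 0.25/0.80 = 0.31. Both give about 80% to 83%. A path of 0.1 means that 0.80×0.1 = 0.08, or 16% of d=0.50, runs through fit.

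**4. County dummies.** With ten counties, an intercept, nine dummies and condition make 11 columns of rank 10, so a condition main effect cannot be estimated. A condition-by-time effect can be, but its standard error has no term for counties differing in change. Assume an ICC of change of 0.01, with 24 patients per county (240/10) or 48 (480/10):

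- Between-county factor: sqrt(1+23×0.01) = 1.109, or sqrt(1+47×0.01) = 1.212.
- Critical-value factor, t on 8 df against normal: 2.306/1.960 = 1.177.
- Ratio of interval widths: 1.30, or 1.43.
- A nominal 5% normal test that omits the between-county term has true size 2×[1−Φ(1.960/1.109)] = 7.7%, or 2×[1−Φ(1.960/1.212)] = 10.6%.

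**The case against.** The strongest reply is that the plan's own inputs nearly support its claim. With d=0.80 on fit, d=0.50 in total and at least half of that running through fit, indirect-effect power is about 80% under the t test. The low values need a weak path. This is correct, and it rules out the reading that Aim 3 is underpowered, which a reader might infer from the bottom of the range. It does not rescue the claim, because the share that runs through fit is unknown and the plan does not assume one.

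A reader might also infer that no indirect-effect power was ever calculated. The documents show only that none is reported. Nor is the arithmetic at fault: the d=0.50 figure is right for what it measures, and section 3.8 does say that it is between Standard and Adapted. Only its placement under Aim 3 misleads.

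One might further infer that the Adapted versus Standard comparison on patient outcomes is absent from the plan. Section 4.1 does refer to analyses of change between these arms to post-treatment and to 6FU, and the mediation model would ordinarily yield total and direct effects. Saying that they will be reported is only a clarification.

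On the county issue, it is fair to reply that the ICC of change is assumed and that the 1.18 critical-value factor would remain with no between-county variation at all. Both points stand. The omission of that variation follows from sections 2 and 4.1 whatever its size.

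**Conclusion.** The concern holds as a mislabelled power claim. Section 3.8 gives Aim 3 a figure that belongs to the Adapted versus Standard difference in patient outcome, and nothing in the documents establishes power for the indirect effect. Under joint significance with a t test that power could lie anywhere from about 24% to about 81%, depending on an unstated fit-to-outcome path. Those values rest on the assumed paths, the carried-over ICC of 0.01 and no attrition. They do not show a shortfall.

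The county-dummy point also holds. The condition-by-time interval leaves out between-county variation in change. If the ICC of change is 0.01, a nominal 5% test runs at about 8% to 11%.

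**What to change.** **(a) Section 3.8.** State that the d=0.50 figure is power for the Adapted versus Standard difference in patient outcome, and whether it counts 30 or 60 patients per county. Then add: *No power is reported for the Aim 3 indirect effect; a non-significant indirect effect will be reported with its 95% interval and not read as evidence against mediation.* Alternatively, supply simulated power for the indirect effect together with the assumed paths.

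**(b) Sections 4.1 and 4.5.** For Adapted versus Standard effects, use an interval that includes between-county variation in change, for example county mean changes compared on 8 df with ten counties, and show the county-dummy model alongside.

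**Clarification in 4.5.** Say that the Adapted versus Standard total and direct effects on PROMIS-SD will be reported beside each indirect effect.

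**Cost.** Text edits and one further analysis of data already being collected. No patients are added; section 6 says that recruitment ended in August 2022. The Aim 3 power claim is given up unless a calculation is supplied. The Adapted versus Standard intervals become wider, by the factors of 1.30 and 1.43 derived above if the ICC of change is 0.01.
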